## 8.2.3 Linear Growth

Linear growth, as measured by height, is a central component of overall growth that is to be described in this cohort of children. Let  $Y_{ij}$  be the age- and gender-normed standard deviation score (SDS) based on the average of two heights measured in cm for child i at visit j, where visit j is taken at time t. The age- and gender-specific norms are derived as  $Y_{ij} = (U_{ij} - \mu) / SD(\mu)$ , where  $U_{ij}$  is the raw average of the two measured heights,  $\mu$  is the age and gender specific mean norm height and SD( $\mu$ ) is the standard deviation of  $\mu$ ; both  $\mu$  and SD( $\mu$ ) are based on tables provided by the National Center for Health Statistics.

A regression of the form  $Y_{ij} = b_0 + b_1t_{ij} + b_2G_{ij} + b_3G_{ij}t_{ij}$ , where the variable  $G_{ij}$  is the decline of GFR in the preceding year scaled to a 5-unit difference (= (GFRij-1 – GFRij)/5), will describe the trajectory of linear growth as a line with intercepts  $b_0$  for those with no GFR decline and  $b_0 + b_2$  for those with a 5 ml/min|1.73m^2 decline in GFR, and slopes  $b_1$  for individuals who have no GFR decline and  $b_1 + b_3$  for those with a 5 ml/min|1.73m^2 decline in GFR. Here, the intercepts describe the initial difference in height SDS due to decline in GFR, and the slopes describe the linear rate of change in height SDS due to decline in GFR (For more detail about the specification of GFR please see section 8.2.2). As with IQ (see section 8.2.2), we will be able to investigate nonlinear growth rates by a polynomial expansion of  $t_{ij}$ , and the statistical dependence of repeated height measurements will be addressed using either mixed effects models or generalized estimating equations.

The above regression will be extended to control for possible confounding by age since diagnosis and caloric intake by the addition of  $b_4A_{ij}$  and  $b_5C_{ij}$ , where  $A_{ij}$  is the percent of a child's age that the child has lived with CKD centered about 50% (= [100(t – age of diagnosis of CKD) / t ] – 50) and Cij is the caloric and/or protein intake measured by Food Frequency Questionnaire. Here  $b_4$  quantifies the shift of the regression line for a one percent increase in age since CKD diagnosis. The parameter  $b_5$  quantifies the effect of a 1-unit increase in caloric and/or protein intake on the shift of the regression line. In this extended model, the slope  $b_1 + b_3$  estimates the effect of a decline of 5 ml/min|1.73m^2 of GFR, independent of age at diagnosis and caloric intake.

To explore potential effect modification, the above extended model will be stratified by the use of growth hormone and/or steroids to assess whether the effect of GFR decline differs in the presence of these therapies.

In addition to linear growth, we will explore changes in body mass and specific biomarkers, such as iPTH over the course of follow up.

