## 6.5.1 Core Tests

The core tests to measure growth are:

- Height/Length
- Body Mass Index
- Circumferences (Head, arm, waist and hip)
- Parathyroid Hormone (intact)
- High Sensitivity C-Reactive Protein
- Vitamin D
- Fibroblast Growth Factor 23 (FGF-23)
- Food Frequency Questionnaire
- Grip Strength

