### 6.5.1.7 Food Frequency Questionnaire (FFQ)

The Food Frequency Questionnaire was completed on a yearly basis beginning at the second baseline visit (V1b). During the study visit, the parents and/or child were instructed to complete the age appropriate FFQ and returned the completed form to the clinical site study coordinator. When the family returns the FFQ to the study coordinator, the study coordinator reviewed the forms for completeness. If there were missing information, the study coordinator clarified with the family and sent the completed FFQs to the Clinical Coordinating Center with the other study forms. As of the June 2014 amendment, the study discontinued collecting FFQ data.

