### 8.2.2 Left Ventricular Thickness

One key outcome for the cardiovascular aim is change in left ventricular (LV) thickness, as measured by echocardiogram at the visit 2 and every other year thereafter. LV thickness will be quantified as the LV mass index in units of g/m2.7. We will also explore use of interventricular and posterior wall thicknesses, but constrain ourselves here to LV mass index. Due to the timing of the echocardiography, we will have approximately 300 children with two measurements of LV thickness during the 1st funding cycle: the analysis described below is restricted to these approximately 300 children.

Let Yi be the 2-year change in LV thickness measured in units of  $g/m^{2.7}$  for child i (= yij - yij-2). We will fit a regression model for the effect of decline in GFR on the change in LV thickness of the form Yi = b0 + b1ti + b2LVi + b3Gi, where ti measures the time between the two echocardiograms, centered at 2 years (= (tij - tij-2) - 2), the variable LVi measures the baseline LV thickness, centered at its mean, and Gi is the decline of GFR in the year preceding the baseline LV measurement scaled to a 5-unit difference (= (GFRij-1 - GFRij)/5). This model will describe the average change in LV thickness as b0 for those with 2 years between echocardiograms, average LV thickness at baseline, and no GFR decline. Individuals with 2-years between echocardiograms and average baseline LV thickness who exhibit a GFR decline of 5 ml/min|1.73m^2 will have an

average change in LV thickness of  $b_0 + b_3$ , such that  $b_3$  quantifies the effect of GFR decline on change in LV thickness.

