The above regression will be extended to control for possible confounding by age since diagnosis, blood pressure and body mass index by the addition of +  $b_4A_i + b_5SBP_i + b_6BMI_i$ , where  $A_i$  is the percent of a child's age that the child has lived with CKD centered about 50% (= [100(t – age of diagnosis of CKD) / t ] – 50), SBP\_i is the average of two clinical systolic blood pressure measurements, and BMI\_i is the child's body mass index. Here  $b_4$  is quantifies the shift of the regression line for a one percent increase in age since CKD diagnosis. For example, in children 12 years of age, those who have had CKD since age 9 versus those who have had CKD since age 6 will differ in Y12 by  $b_4[100x(6/12 - 3/12)]= 25b_4$ . The parameters  $b_5$  and  $b_6$  quantify the effects of a 1-unit increase in systolic blood pressure and body mass index on the shift of the regression line, respectively. In this extended model,  $b_3$  estimates the effect of a decline of 5 ml/min[1.73m^2 of GFR, adjusting for age at diagnosis, systolic blood pressure, and body mass index.

To explore potential effect modification, the above extended regression model will be stratified by the use of ACE inhibitors and/or quintiles of sodium intake, as measured with a food frequency questionnaire, to assess whether the effect of GFR decline on change in LV thickness differs in the presence of this therapy or salt intake.

Of course, more detailed analysis plans and further delineated analytic models will be possible as data accumulates and hypotheses develop. For instance, the Cardiovascular Subcommittee has expressed interest in the analysis of repeated measurements of clinical blood pressures as well as episodes of nocturnal 'dipping' blood pressure available from ambulatory blood pressure monitoring.

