### 2016

Mid March:Two-Day CKiD Meeting with Investigators and CoordinatorsLate April:Second Annual CKiD WorkshopLate Sept:Began recruitment of non-glomerular children with less than 5 years CKD
duration (Cohort 3)

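### The adjusted growth model in 8.2.3 needs food-frequency intake that stopped being collected in June 2014, so it drops all of Cohort 3 and every later Cohort 1 and 2 visit, while the unadjusted model keeps them

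*Protocol*

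**What the plan says.** Section 8.2.3 (Linear Growth) first gives an unadjusted regression of height SDS on time, GFR decline over the preceding year (`G_ij`) and their product. It then says that this regression will be extended by two confounders. One is `A_ij`, the share of the child's life spent with CKD. The other is `C_ij`, which "is the caloric and/or protein intake measured by Food Frequency Questionnaire". Both carry the child and visit subscripts. Effect modification by growth hormone or steroids is to be examined by stratifying this extended model, not the unadjusted one.

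Section 6.5.1.7 describes the questionnaire in the past tense: "The Food Frequency Questionnaire was completed on a yearly basis beginning at the second baseline visit (V1b"). It closes with "As of the June 2014 amendment, the study discontinued collecting FFQ data". The list of core growth tests in 6.5.1 still contains "Food Frequency Questionnaire" with no note that it has ended.

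Appendix D has this entry for late September 2016: "Began recruitment of non-glomerular children with less than 5 years CKD" duration, which it labels Cohort 3. Section 5.4 plans 190 such children, and annual in-person visits for about 13 years.

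**The concern.** A mixed model or GEE, the two methods named for this regression, uses only records in which every covariate is present. If `C_ij` is a model term, each record without it is lost. Here the loss is not sporadic. It is fixed by calendar date and by cohort.

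Two things are at stake. First, the adjusted growth answer would come from older Cohort 1 and 2 visits only, with nothing from the cohort recruited to fill the gap described in 9.1 (non-glomerular disease followed from early in its course). Second, the crude model would still use all cohorts and visits. A reader who compares crude and adjusted slopes to judge confounding would be comparing different children at different times.

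**Working it through.** The protocol gives no sample size or power figure for this model, so there is none to reproduce. The check is one of dates and counts.

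**Inputs**

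| Item | Value | Place |
|---|---|---|
| FFQ collection ended | June 2014 amendment | 6.5.1.7 |
| Cohort 3 recruitment began | late September 2016 | Appendix D |
| Cohort 1 enrolled | 586 | 9.1 |
| Cohort 2 enrolled | 305 | 9.1 |
| Cohort 3 planned | 190 | 5.4, 9.1 |
| First annual visit after baseline (V2) | one year after V1a | 5.4 |

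**Step 1: children.** Cohort 3 began more than two years after the FFQ ended, so no Cohort 3 child can have a `C_ij` value. The share is 190 / (586 + 305 + 190) = 190 / 1,081 = 17.6%. At most 1,081 − 190 = 891 children can enter the adjusted model.

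**Step 2: is there another source of intake?** The and/or in the definition of `C_ij` gives no way out, because calories and protein both come from the FFQ. Section 6.1.5 (Assessment of Dietary Intake) now covers only herbal remedies, supplements and vitamins. The table of variables affecting growth in 6.5.3 has no intake variable. Section 7.4.4 names albumin, BMI and cholesterol as the core nutrition measures.

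**Step 3: visits.** All Cohort 1 and 2 visits after June 2014 also lack `C_ij`. The model further needs `G_ij`, so a child's first usable record is at about V2. A child whose V1a fell after about mid-2013 therefore has no record carrying both terms. Appendix D closes Cohort 2 glomerular enrolment in early May 2014 and non-glomerular enrolment at least a year earlier, so this extra loss falls mainly on the glomerular group.

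**Step 4: share of visits, as an illustration only.** The protocol does not give visit counts. Assume no attrition, annual visits from one year after entry, and uniform enrolment over 2005.25–2009.6 (Cohort 1), 2011.0–2014.35 (Cohort 2) and 2016.75–2018.75 (Cohort 3), with the FFQ stopping at 2014.45.

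| Visits counted up to | Cohort 1 with FFQ / all | Cohort 2 | Cohort 3 | Total | Without FFQ |
|---|---|---|---|---|---|
| 2017.6 | 3,825 / 5,686 | 396 / 1,352 | 0 / 0 | 4,221 / 7,038 | 2,817 / 7,038 = 40% |
| 2018.6 | 3,825 / 6,272 | 396 / 1,657 | 0 / 81 | 4,221 / 8,010 | 3,789 / 8,010 = 47% |

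Attrition removes later visits more than earlier ones, so in Cohorts 1 and 2 it would lower these shares. They show the order of size and are not estimates.

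**Step 5: the crude model.** It contains only time and `G_ij`. Iohexol GFR is optional in Cohort 3, but serum creatinine is measured every year and 8.2.1 allows GFR to be estimated from it. Nothing in the unadjusted model therefore excludes Cohort 3 or visits after June 2014.

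**The case against.** The strongest reply is that section 8.2 is headed as examples and that 8.2.2 expects analysis plans to be refined as data accumulate. No passage calls the FFQ-adjusted model the main growth analysis, the unadjusted model is untouched, and the study's primary scientific goal is risk factors for GFR decline. This stands and it limits the severity. It does not remove the contradiction: the introduction to 8.2 presents these as specific analyses, and 8.2.3 commits to the extension without limiting the population.

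A second reply is that section 8.1.1 chooses methods that accept incomplete and unbalanced data. That covers missing outcomes and unequal numbers of visits. It does not recover a covariate that was never collected in a whole cohort. A separate analysis plan may name a substitute, but 8.2.3 does not.

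Three stronger readings are tempting, and the protocol does not support them.

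- A reader might infer that the left ventricular analysis in 8.2.2 fails in the same way, because it mentions "quintiles of sodium intake, as measured with a food frequency questionnaire". It does not. That section says "the analysis described below is restricted to these approximately 300 children", meaning children with two measurements in the first funding cycle, and Appendix D shows first-cycle data deposited in October 2013, before the FFQ ended. The model there is to be "stratified by the use of ACE inhibitors and/or quintiles of sodium intake, as measured with a food frequency questionnaire", so sodium is an optional stratifier and not a model term. The end of the FFQ removes no child or visit from that analysis.
- A reader might infer that no child with early disease is left in the adjusted growth model. Section 9.1 describes Cohort 2 as having early CKD, and 8.1.2 says that children with glomerular disease are more likely to enter soon after diagnosis. Part of that cohort has FFQ data.
- A reader might infer that little usable FFQ data exists. Cohort 1 baseline visits ran from 2005 to August 2009, which leaves roughly 5 to 9 years of annual questionnaires before June 2014.

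**Conclusion.** The point holds for the adjusted growth model and for the growth-hormone and steroid strata that use it. As written, these exclude all 190 Cohort 3 children (17.6% of 1,081) and all Cohort 1 and 2 visits after June 2014. The crude model keeps those children and visits, so the two sets of estimates are not comparable.

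The 17.6% rests on the enrolled numbers for Cohorts 1 and 2 and the planned number for Cohort 3. The exclusion itself rests only on dates that the protocol states. The 40% to 47% of visits depends on the enrolment and attrition assumptions shown above.

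This should be corrected, but it does not threaten the study: it concerns an example analysis for the growth aim. The FFQ entry in the 6.5.1 list is a clerical leftover, since 6.5.1.7 states the discontinuation openly.

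**What to change.** In 8.2.3:

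1. Remove `C_ij` from the adjusted model fitted to all cohorts and visits, and keep `A_ij`. Build the growth-hormone and steroid strata on this model.
2. Keep the FFQ-adjusted model as a sensitivity analysis, limited to Cohort 1 and 2 visits up to June 2014. Refit the models without `C_ij` on exactly the same records, so that any change in the estimates reflects adjustment and not a change of population.
3. If some control for nutrition is wanted in all cohorts, add serum albumin, which 6.2.1.10 schedules at baseline and every annual visit, as a further sensitivity analysis. It should not be the default: 6.5.3 pairs it with urine protein, and it may lie on the path from GFR decline to growth. BMI should not be the default substitute either, because height is in its denominator and the outcome is height SDS.

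As a tidy-up, mark the FFQ as discontinued in the 6.5.1 list.

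No new data are needed and the text changes are short. The real cost is that dietary intake is not controlled in the all-cohort model. The restricted sensitivity analysis shows how much that matters in the children and visits where intake was recorded, but it cannot show it for Cohort 3.

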To address these challenges, the study recruited an additional 305 children with early CKD (hereafter referred to as Cohort 2). Of the 305 children, 147 had glomerular and 158 non-glomerular diagnoses. It is expected that 90% and 85% of those recruited with glomerular and non-glomerular diagnoses will remain in the study, providing data for estimating GFR change, based on the current observed data in 55 glomerular and 197 non-glomerular subjects in Cohort 1 with a baseline eGFR > 45 ml/min/1.73m^2. Hence,

recruiting 147 children with a glomerular diagnoses and 158 children with a nonglomerular diagnoses will achieve a power of at least 70% to detect differential rates of GFR decline according to by uP/C strata (above or below 0.5) among those with an initial eGFR between 45 and 90 ml/min/1.73m^2.

Other potential biomarkers such as microalbuminuria will be explored. Preliminary data show that 75% of Cohort 1 has urine microalbumin > 30 mg/g creatinine. It is estimated that the presence of microalbuminuria in Cohort 2, which is a cohort of children with milder CKD will be lower (around 30 %). If 12.5% of the children with non-glomerular diagnoses, an eGFR from 45 to 90 ml/min/1.73m^2 and without microalbuminuria progress to renal failure during follow-up, the study will have 80% power to detect a risk ratio of 2.0 in children associated with microalbuminuria, with 90% confidence.

Additionally in the Cohort 2 children with glomerular diagnoses, investigators will have the ability to detect an increased risk of developing dyslipidemia associated with GFR decline >10% per year. If among children with glomerular diagnoses, 50% decline at > 10% per year, the study will have 80% power to detect an increased risk for the development of dyslipidemia associated with a risk ratio of 3.0 in those with a more rapid compared to those with a slower GFR decline (assuming a risk of dyslipidemia of 10% in those with slow GFR decline).

The CKiD study has contributed substantially to the knowledge of chronic kidney disease in children. However, even with the enrollment of Cohorts 1 and 2, gaps exist in the overall cohort as it stands. Enrollment of an additional cohort of 190 children with non-glomerular kidney disorders (Cohort 3) from early in their course of disease will facilitate characterization of the progression of CKD in this previously understudied population. Targeting children close to disease onset will enhance our ability to accomplish the aims of the CKiD study, respond to the needs identified to maximize the impact of research in the Kidney Research National Dialogue (KRND) initiative, and improve the long term outcomes for children with kidney disease. We based our sample size calculation on determining the size of the cohort that we will need to have p/2 precision if the true rate of a condition of interest (e.g., acidosis) is p. In other words, since the 95% confidence interval for p is  $p\pm 1.96\sqrt{p(1-p)/n}$ , the sample size n is determined by requiring  $1.96\sqrt{p(1-p)/n}$  to be equal to p/2 (e.g., if p is 0.05, n will yield a 95% CI from 0.025 to 0.075). For p= 5%, 7.5% and 10%, the corresponding n's will be 292, 190 and 138, respectively. Although the desired sample size will be 292 in each group (i.e., to estimate 5% with ±2.5% precision), this will amount to the recruitment in wave 3 of a cohort to be of the same size as the cohort recruited in wave 1 and will require longer than 2 years to recruit. Hence, we will recruit 190 children with a Non-Glomerular diagnoses.

### 9.2 Time-to-Event Analyses

We have presented power calculations for proposed investigations into the impact of GFR decline on disease outcomes using longitudinal analysis methods. Alternatively,

analyses comparing the time to an event of interest will also be utilized, when appropriate, for outcomes such as ESRD. Table 9.2 shows the rate ratio thresholds that will be detectable with 80% statistical power at a 5% significance level according to three possible incidence rates among the unexposed (3, 6, and 9 events per 100 person-years) and by three levels of exposure prevalence (20%, 30% and 40%). Specifically, given an incidence of 6 per 100 person-years among the

Table 9.2

Detectable rate ratios with 80% power at 5% significance level

	Incidence among the unexposed:			
% exposed:	3 per 100 py *	6 per 100 py *	9 per 100 py *	
20 %	2.52	2.00	1.79	
30 %	2.28	1.85	1.68	
40 %	2.19	1.79	1.63	

\* py = person-years

unexposed and 30% exposure prevalence we will have 80% power to detect a rate ratio of 1.85. However, if composite events were defined, such as in the AASK study, as (i) ESRD, (ii) a  $\geq$  50% decline in GFR, or (iii) a decline of at least 25 ml/min|1.73m^2, higher rates among the unexposed would be expected, resulting in greater statistical power.

## 10. STUDY MANAGEMENT

## 10.1 Training

The DCC will assist and oversee the clinical coordinating centers to conduct training meetings for study investigators to review study design, consent procedures, patient recruitment and enrollment, data collection forms and schedules, test procedures and reporting. Study personnel from each of the clinical sites will be required to demonstrate proficiency in knowledge of the protocol for certification. Personnel will be complete an online knowledge assessment test and required to obtain a passing grade of 85%. All new coordinators who replace existing coordinators will be trained at their clinical sites and/or by their respective CCC. As such, the coordinators who review the DVDs will also be required to take the online knowledge assessment test and obtain a passing grade of 85%. Appendix D outlines the study timeline which includes training all participating clinical staff in the CKiD protocol, obtaining IRB approval from participating sites, etc.

Data management staff from the clinical coordinating centers will come to the DCC for training on the use of the web-based system. The web-based system is menu driven. New data management staff who replace staff trained at the DCC will be trained at their respective CCC. The DCC recommends data entry be performed by the sample person or people who are familiar with study forms.

## 10.2 Conference Calls and Site Visits

Over the course of the study, we plan to conduct conference calls with the principal investigators and coordinators to review recruitment and data quality. The DCC will also conduct site visits to each clinical coordinating center. We will conduct site visits for the purpose of observing operations, assessing adherence to protocols and certifying staff examination of procedures and interviews. It will also be an opportunity to obtain feedback regarding the protocol and their interaction with the DCC, clinical coordinating centers, the central laboratories and the repositories. This report will summarize findings as well as suggested changes for study-wide protocols.

# 10.3 Monitoring Study Conduct and Scientific Progress

10.3.1 Bi-monthly Steering Committee Conference Calls

The SC will meet by conference call bi-monthly, as arranged by the DCC. Bi-monthly conference calls will address issues of study conduct, including recruitment and retention, as well as scientific progress via review of concept sheets and draft manuscripts.

10.3.2 Semi-Annual Steering Committee and Annual Investigator/Coordinator Meetings The SC and invited guests will meet in person two times per year. Additional meetings will be scheduled as needed during the recruitment and retention phases of CKiD. On an annual basis, a two day meeting will be held, and will roughly track the following agenda:

Day 1 (Steering Committee Meeting or Specific study procedure training)
8:30 – 12:00Data report; study-wide subcommittees or procedural
training (i.e., vascular testing)12:00 – 1:00
1:00 – 5:00Working lunch
Novel scientific presentations; subcommittee related to
specific aims of CKiD

Day 2 (Investigator/Coordinator Meeting)

8:30 - 12:00	Scientific progress and priorities
12:00 – 3:00	Protocol Changes and Scientific Discussions

The data report will include sections on (1) recruitment and retention, (2) comprehensive summaries of data according to scientific aims of CKiD, (3) overall report on data quality, and (4) reports in regards to the central laboratories, central reading centers, and central repositories. The novel scientific presentations will include reports of proposed or accepted concept sheets and/or invited symposium on a specific scientific topic of interest. The protocol changes meeting will comprise discussions and decisions regarding alterations in the study protocol. Finally, scientific progress and priorities will assess the progress of every active concept sheet by roll call and rank order the CKiD scientific priorities over the subsequent six months, respectively.

